## 5.2. Participant Dispositions

The number of participants screened, and the number of participants screen failed will be summarized for all enrolled participants.

The number of participants in the following disposition categories will be summarized throughout the study by intervention group and overall based on Full Analysis Set:

- Participants randomized
- Participants who received study intervention
- Participants who completed the study
- Participants who discontinued study intervention
  - Reasons for discontinuation of study intervention
- Participants who terminated study prematurely
  - Reasons for termination of study

The above categories will include summaries over the placebo-controlled period (through Week 16) and the entire study (through Week 36).

Listings of participants will be provided for the following categories:

- Participants who discontinued study intervention
- Participants who terminated study prematurely
- Participants who were unblinded during the study period
- Participants who were randomized yet did not receive study intervention. Participants who were randomized with incorrect stratum.

## 5.3. Primary Endpoint Analysis

### 5.3.1. Definition of Endpoint(s)

The primary efficacy endpoint is the proportion of participants achieve a HiSCR50 at Week 16 in Part 1. HiSCR50 is defined as a  $\geq 50\%$  reduction in inflammatory lesion AN count (sum of

abscesses and inflammatory nodules), and no increase in abscesses and draining fistulas in HS compared with the lesions counted at baseline.

### 5.3.2. Estimand

An estimand is a precise definition of the primary targeted treatment effect defined by the following 5 attributes: Study Intervention, population, variable (endpoint), intercurrent events (ICEs) and corresponding strategies, and population-level summary.

**Primary Trial Objective:** to evaluate the efficacy of bermekimab in participants with moderate to severe HS.

**Estimand Scientific Question of interest:** What is the proportion of participants considered to have benefited from bermekimab versus placebo assessed by the HiSCR50 at Week 16 in Part 1, administered together with the protocol allowed background standard-of-care medication.

#### 5.3.2.1. Primary Estimand (Composite Estimand)

- **Study intervention:**
  - Bermekimab 1050 mg
  - Placebo
- **Population:** adult participants with moderate to severe HS
- **Variable/endpoint:** Response binary variable, where a responder is defined as a participant achieving an HiSCR50 response at Week 16 in Part 1 without experiencing any of the ICEs in categories 1-2 as outlined below prior to the Week 16 visit.

Intercurrent Events (ICEs)	Analysis Strategy for Intercurrent Events
1. Discontinuation of study intervention due to lack of efficacy, an AE of worsening of HS	Composite Strategy: Participants with these intercurrent event are considered as HiSCR50 non-responders after these events, and prior to Week 16, as reflected in variable definition.
2. Initiation of a protocol-prohibited medication or therapy during the study that could improve H S	
3. Discontinuation of study intervention for reasons other than ICE 1	Treatment Policy: observed data will be used regardless of whether or not this intercurrent event had occurred.

Note: For participants experiencing multiple ICEs, ICE 2 will override ICE 3.

The composite strategy assesses the treatment effects not only based on the variable measurements, but also based on ICEs. This estimand acknowledges that having an ICE in categories 1-2 is an unfavorable outcome. For participants experiencing an ICE in category 3, the treatment policy

strategy considers the occurrence of ICE 3 irrelevant in defining the treatment effect, and any data observed after the associated ICE event will be used for the analysis.

**Population level summary:** Difference in the proportions of participants achieving an HiSCR50 response at Week 16 between the bermekimab 1050 mg and placebo intervention groups.

### **5.3.2.2. Supplementary Estimand (Treatment Policy Estimand):**

The supplementary estimand has the same components as the primary estimand, except for the strategy used below for ICEs 1-3.

**Treatment policy strategy:** assess the treatment effect regardless of whether or not intercurrent events had occurred. Under the treatment policy strategy, observed data collected after ICEs will be used in analysis.

### **5.3.3. Analysis Methods for the Primary Estimand**

The primary endpoints will be analyzed based on the composite estimand (Section 5.3.2.1) and the data from all participants in mFAS (Section 4.4) will be analyzed according to randomized treatment group regardless of the treatment actually received. Participants whose projected Week 16 visits occur after study termination will be excluded in the primary analysis. Participants with ICEs 1-2 before Week 16 will be considered as HiSCR50 non-responders at Week 16. Participants with ICE 3, observed lesion data after this ICE will be utilized in the analysis. For participants experiencing multiple ICEs, an ICE 2 will override an ICE 3. After accounting for the ICEs for the primary estimand, the remaining missing data of the primary endpoint at Week 16 will be considered as a non-responder.

In this primary analysis, the proportion of participants who achieve a HiSCR50 at Week 16 will be summarized for each treatment group. To address the primary objective, a CMH chi-squared statistic stratified by baseline Hurley stage status (II, III) at an alpha level of 0.1 will be used for each of the comparisons between bermekimab treatment groups and placebo group. The comparison between adalimumab and placebo for the primary endpoints will also be performed. Difference in response rates between each of the active groups and the placebo group adjusted for baseline Hurley stage status (II, III) using Mantel-Haenszel weight and the corresponding 90% CI will be presented.

In addition, the proportion of participants achieving a HiSCR50 response at Week 16 by investigator regions and site will be summarized.

### **5.3.4. Analysis for Supplementary Estimand (Treatment Policy Estimand)**

To examine the robustness of the primary endpoint analysis, the primary endpoint will be analyzed utilizing the treatment policy estimand. For participants who experience an intercurrent event, the analysis will be performed using observed data regardless of intercurrent events. The HiSCR50 values collected after intercurrent event will be used in analysis and missing data will not be imputed.

## 5.4. Secondary Endpoints Analysis

### 5.4.1. Multiplicity Adjustment for Testing Procedures

No multiplicity adjustments will be made for the secondary endpoints. All statistical testing will be performed at the 2-sided 0.1 significance level. Nominal p-values will be presented.

### 5.4.2. Definition of Secondary Endpoints

#### 5.4.2.1. Hidradenitis Suppurativa Clinical Response (HiSCR)

- HiSCR75 is defined as a  $\geq 75\%$  reduction in inflammatory lesion AN count (sum of abscesses and inflammatory nodules) from baseline and no increase in abscesses or draining fistulas in HS compared with the lesions counted at baseline.
- HiSCR90 is defined as a  $\geq 90\%$  reduction in inflammatory lesion AN count (sum of abscesses and inflammatory nodules) from baseline and no increase in abscesses or draining fistulas in HS compared with the lesions counted at baseline.

Please also refer to Section **Error! Reference source not found.** for the definition of the HiSCR50 responder status.

#### 5.4.2.2. Lesion Count

Lesion counts are defined as the number of abscesses, inflammatory nodules, non-inflammatory nodules, draining fistulas, and non-draining fistulas respectively. Lesions will be counted during each visit. AN count is defined as total abscess and inflammatory nodule count.

#### 5.4.2.3. International Hidradenitis Suppurativa Severity Score System (IHS4)

IHS4 is a dynamic severity assessment of HS. IHS4 score is arrived at by the number of nodules (multiplied by 1) plus the number of abscesses (multiplied by 2) plus the number of draining tunnels (multiplied by 4). A total score of 3 or less signifies mild, 4-10 signifies moderate and 11 or higher signifies severe disease.

#### 5.4.2.4. Hidradenitis Suppurativa Investigator's Global Assessment

The HS-IGA documents the investigator's assessment of the participant's HS at a given timepoint. The anatomic region with the most severe HS activity at the baseline visit should be evaluated for erythema, drainage, and pain and/or tenderness to palpation for each participant. For each participant, the same anatomic site selected for evaluation at the baseline visit should be re-evaluated at each subsequent visit. The participant's HS is assessed as inactive (0), almost inactive (1), mild activity (2), moderate activity (3), or severe activity (4). A higher score indicates more severe disease.

#### 5.4.2.5. Hidradenitis Suppurativa Symptom Diary (HSSD)

The HSSD is an 8-item patient self-reported questionnaire that assesses symptoms (including pain, tenderness, pressure, itch, heat, and odor) and signs (including swelling and drainage) of HS. The participants are asked to rate the severity of each symptom on a 0 to 10 numerical rating scale, with 0 indicating no symptom experience and 10 indicating the worst possible symptom

experience. Two versions are available: one with a 24-hour recall (HSSD-24h) and one with a 7-day recall (HSSD-7d). Each individual symptom (including pain and itch) and sign scale score, ranging from 0-10, will be summarized. A total symptom score will be derived by averaging the 6 individual symptom scale scores. A total sign score will be derived by averaging the 2 individual sign scale scores. An overall total score will be derived by averaging all 8 individual items. The last item included in the HSSD is an optional item for patients to assess systemic symptoms of HS (flu-like symptoms). It will be assessed as a separate item and not included in HSSD overall total score. The psychometric properties of the HSSD will be evaluated for scale validation using the data from this study.

For the HSSD-24h rating scale, each component will be averaged into a weekly score respectively (ie 7 days [from day -7 to -1] prior to a visit). Four days out of 7 days (either consecutive or nonconsecutive) are necessary to derive a weekly score; otherwise data are considered missing for that week. The baseline is defined as the average score of last 7 days prior to Week 0 study agent administration. Similarly, if there are more than 3 days missing data, then baseline is set as missing. Missing baseline will not be imputed.

### 5.4.3. Estimands for Secondary Endpoints

The secondary endpoints will be analyzed using the same attributes as the primary estimand described in section 5.3.2.1 except for the Variable (Endpoint) definition. The estimands for secondary endpoints will be considered for both binary and continuous secondary endpoints.

- **Study intervention:**
  - Bermekimab 1050 mg
  - Placebo
- **Population:** adult participants with moderate to severe HS
- **Population level summary:** Difference in the proportions of participants achieving a binary response, or difference in change from baseline of a continuous endpoint at Week 16 between the bermekimab 1050 mg and placebo intervention groups.
- **Variable/endpoint:** variables defined as below, without experiencing any of the ICEs in categories 1-2 prior to the Week 16 visit.

### BINARY ENDPOINTS

**Variable (endpoint):** Binary response variable (response/non-response) with response defined as follows at Week 16.

- The proportion of participants who achieved HiSCR75 and HiSCR90
- The proportion of participants with HS-IGA score of inactive (0), almost inactive (1), or mild (2) and with at least 2-grade improvement relative to baseline

## CONTINUOUS ENDPOINTS

**Variable (endpoint):** Continuous variables of change from baseline at Week 16 as defined below.

- The change from baseline in AN count
- The change from baseline in number of abscesses
- The change from baseline in number of draining fistulas
- The change from baseline in number of inflammatory nodules
- The change from baseline in international hidradenitis suppurativa severity score (IHS4)
- The change from baseline in pain scale score of HSSD-24h

Intercurrent Events (ICEs)	Analysis Strategy for Intercurrent Events
1. Discontinuation of study intervention due to lack of efficacy, an AE of worsening of HS 2. Initiation of a protocol-prohibited medication or therapy during the study that could improve H S	Composite Strategy: Participants with these intercurrent event are considered as non-responders for binary endpoints and zero change from baseline for continuous endpoints after these events, as reflected in variable definition.
3. Discontinuation of study intervention for reasons other than ICE 1	Treatment Policy: observed data will be used regardless of whether or not this intercurrent event had occurred.

Note: For participants experiencing multiple ICEs, ICE 2 will override ICE 3.

### 5.4.4. Analysis Methods for Secondary Endpoints

The secondary endpoints at Week 16 will be analyzed using the estimand described in section 5.4.3 for mFAS. The endpoints will be summarized by intervention group. Simple descriptive statistics, such as n, mean, SD, median, IQ range, minimum and maximum for continuous variables and counts and percentages for discrete variables will be used to summarize the data.

### Binary Endpoints

- The proportion of participants who achieved HiSCR75 and HiSCR90 at Week 16 in Part 1 will be compared between the bermekimab groups and the placebo group.
- The proportion of participants with HS-IGA score of inactive (0), almost inactive (1), or mild (2) and with at least 2-grade improvement relative to baseline at Week 16 in Part 1 will be compared between the bermekimab groups and the placebo group.

The analysis strategy for ICEs and missing data for binary endpoints will be handled in the same manner as the primary estimand for the primary analysis. The Cochran-Mantel-Haenszel chi-square statistic stratified by baseline Hurley stage status (II, III) at a 2-sided significance level of 0.1 will be used. Difference in response rates between each of the active and placebo groups at Week 16 adjusted for baseline Hurley stage status (II, III) using Mantel-Haenszel weight and the corresponding 90% CI will be presented.

In case of rare events, the Fisher's Exact test will be used for treatment comparisons in binary response endpoints. The proportion differences between active treatment groups and placebo and the exact confidence intervals will be provided.

### Continues Endpoints

- The change from baseline in AN count at Week 16 in Part 1 will be compared between the bermekimab groups and the placebo group.
- The change from baseline in number of abscesses at Week 16 in Part 1 will be compared between the bermekimab groups and the placebo group.
- The change from baseline in number of draining fistulas at Week 16 in Part 1 will be compared between the bermekimab groups and the placebo group.
- The change from baseline in international hidradenitis suppurativa severity score (IHS4) at Week 16 in Part 1 will be compared between the bermekimab groups and the placebo group.
- The change from baseline in number of inflammatory nodules at Week 16 in Part 1 will be compared between the bermekimab groups and the placebo group.
- The change from baseline in pain scale score of HSSD-24h at Week 16 in Part 1 will be compared between the bermekimab groups and the placebo group.

Unless otherwise specified, the analyses for continuous secondary endpoints at Week 16 will be based on the following strategies to handle ICEs and missing data.

- Participants experiencing ICEs 1-2 will have a zero change from baseline assigned from that point onward.
- The analysis for participants with ICE3 will be performed using observed data regardless of intercurrent events. For participants experiencing multiple ICEs, an ICE in categories 2 will override an ICE in category 3.
- Missing data will not be imputed after applying the rules for intercurrent events, and missing data will be accounted for through correlation of repeated measures in the Mixed-Effect Model Repeated Measure (MMRM) model.

Treatment comparisons for the secondary continuous endpoints at Week 16 will be performed using a MMRM model under the assumption of missing at random (MAR) with intervention group, visit, baseline Hurley stage status (II, III), baseline value for the efficacy endpoint, treatment by visit, baseline Hurley stage by visit and baseline value by visit interaction as explanatory factors, if appropriate. An unrestricted (UN) variance-covariance matrix for repeated measures within a participant will be used. If the model with unstructured covariance structure does not converge, alternative covariance structures will be tried in the following order, with the first structure that converges being used in the analysis: heterogeneous Toeplitz, standard Toeplitz, and autoregressive of order 1.

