#### **5.1. Inclusion Criteria**

Each potential participant must satisfy all of the following criteria to be enrolled in the study:

1. Be a male or female 18 (or the legal consent in the jurisdiction in which the study is taking place) years of age or older.
2. Be otherwise healthy on the basis of physical examination, medical history, vital signs, and 12-lead ECG performed at screening. Any abnormalities, must be consistent with the

underlying illness in the study population and this determination must be recorded in the participant's source documents and initialed by the investigator.

3. Have HS for at least 1 year (365 days) prior to the baseline visit as determined by the investigator through participant interview and/or review of the medical history.
4. Have HS lesions present in at least 2 distinct anatomic areas (examples include but are not limited to left and right axilla; or left axilla and left inguocrural fold) at screening and baseline visits.
5. Have Hurley Stage II or Hurley Stage III HS as determined by the investigator at screening and baseline visits.
6. Had an inadequate response to a course of appropriate oral antibiotics for treatment of HS (or demonstrated intolerance to or had a contraindication to oral antibiotics for treatment of their HS) in the investigator's opinion.
7. Criterion modified per Amendment 2.

7.1. Be considered, in the opinion of the investigator, a suitable candidate for adalimumab (HUMIRA®) therapy according to their country's approved HUMIRA product labeling. This criterion only applies to participants enrolling in Part 1 of the study, where adalimumab is one of the possible randomization arms. This criterion does not apply to participants enrolling in Part 2.

8. Have stable HS for at least 60 days prior to the screening visit and at baseline as determined by the investigator through patient interview and/or review of the medical history.
9. Have a total AN count of  $\geq 5$  at the screening and baseline visit.
10. Have screening laboratory test results within the following parameters, if one or more of the laboratory parameters is out of range, a single retest of laboratory values is permitted:
  - a. Hemoglobin  $\geq 10$  g/dL (SI:  $\geq 100$  g/L)
  - b. White blood cells  $\geq 3.5 \times 10^3/\mu\text{L}$  (SI:  $\geq 3.5$  GI/L)
  - c. Neutrophils  $\geq 1.5 \times 10^3/\mu\text{L}$  (SI:  $\geq 1.5$  GI/L)
  - d. Platelets  $\geq 100 \times 10^3/\mu\text{L}$  (SI:  $\geq 100$  GI/L)

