20. The participant is deemed ineligible according to the following TB screening criteria:
  - A diagnosis of active TB is made.
  - A participant has symptoms suggestive of active TB based on follow-up assessment questions and/or physical examination or has had recent close contact with a person with active TB and cannot or will not continue to undergo additional evaluation.
  - A participant undergoing evaluation has a chest radiograph with evidence of current active TB and/or a positive QuantiFERON-TB® (or T-SPOT® for sites in Japan) test result (and/or a positive tuberculin skin test result in countries in which the QuantiFERON-TB® test is not approved/registered or the tuberculin skin test is mandated by local health authorities), unless active TB can be ruled out and appropriate treatment for latent TB can be initiated prior to the next study intervention administration and continued to completion (see also Section 8.2.8.1 and Section 10.8). Indeterminate QuantiFERON-TB® (or

borderline T-SPOT® for sites in Japan) test results should be handled as described in Section 8.2.8.1. Participants with persistently indeterminate QuantiFERON-TB® (or borderline T-SPOT® for sites in Japan) test results may continue without treatment for latent TB if active TB is ruled out, their chest radiograph shows no abnormality suggestive of TB (active or old, inactive TB) and the participant has no additional risk factors for TB as determined by the investigator. This determination must be promptly reported to the medical monitor or designee and recorded in the participant's source documents and initialed by the investigator.

- A participant receiving treatment for latent TB discontinues this treatment prematurely or is noncompliant with the therapy.
21. Has received an immunomodulating biology therapy within the previous 3 months of study intervention administration (including, but not limited to, anti-cytokine, anti-complement antibodies, anti-Ig antibodies, etc).
  22. Has received phototherapy or any systemic medications/treatments that could affect HS or IGA evaluations within 4 weeks of the first administration of any study intervention.
  23. Has any other active skin disease or condition (e.g., bacterial, fungal or viral infection) that could have interfered with assessment of HS.
  24. Has a draining fistula count of >20 at the baseline visit.

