A participant will not be automatically withdrawn from the study if he or she must discontinue treatment before the end of the treatment regimen. Participants who discontinue study intervention but do not terminate study participation will continue to return for protocol-specified procedures and evaluations for approximately 5 weeks following the last administration of study intervention. The procedures and evaluations listed for the Early Termination Visit should also be performed approximately 5 weeks after the last administration of study intervention.

All procedures and evaluations must be conducted prior to a participant's withdrawal of consent.

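### Does scoring zero change after treatment failure distort the continuous secondary endpoints enough to need another analysis?

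*SAP*

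**What the plan says.** SAP 5.4.3 sets out a composite strategy for ICEs 1-2. Binary endpoints become non-response, and continuous endpoints take "zero change from baseline for continuous endpoints after these events, as reflected in variable definition". SAP 5.4.4 repeats this for the model-based analysis: "Participants experiencing ICEs 1-2 will have a zero change from baseline assigned from that point onward". The endpoints are AN count, abscesses, draining fistulas, inflammatory nodules, IHS4 and HSSD-24h pain, each analysed at Week 16 with an MMRM.

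ICE 1 is "Discontinuation of study intervention due to lack of efficacy, an AE of worsening of HS"; ICE 2 is starting a prohibited therapy that could improve HS. SAP 5.3.2.1 explains that either event counts as an unfavourable result. Section 5.4.3 carries over the primary estimand but leaves the variable free to differ: "The secondary endpoints will be analyzed using the same attributes as the primary estimand described in section 5.3.2.1 except for the Variable (Endpoint) definition".

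The one supplementary estimand (SAP 5.3.2.2 and 5.3.4) is treatment policy, and it is for HiSCR50 only: "The HiSCR50 values collected after intercurrent event will be used in analysis and missing data will not be imputed". The over-time summaries in SAP 5.5.2 handle ICEs as the secondary endpoints do.

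**The concern.** A composite value should be unfavourable for everyone who receives it, and zero change fails that test in two situations.

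- **Worsened participants.** ICE 1 includes stopping because HS got worse. Someone whose count went from 5 to 9 has an observed change of +4 but is recorded as 0, better than what happened.
- **Participants who start at 0.** They cannot improve further, so zero is their best attainable score. A treatment failure then ties with the best outcome.

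If failures are more common in one arm, the Week 16 difference moves by an amount set by the rule and not by the data. Because the supplementary analysis stops at HiSCR50 and the over-time summaries reuse the rule, no table shows these endpoints without the assigned values. With roughly 25 to 50 participants per arm, a handful of assigned values could matter to a small mean change.

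**Working it through.** The plan states no rate, mean or SD for these endpoints, so there is no figure to reproduce; its power tables concern HiSCR50.

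**Consistency.** SAP 5.4.3 and 5.4.4 give the same rule. Because 5.4.3 exempts the variable definition from the primary estimand's attributes, there is no conflict with 5.3.2.1.

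**Where zero is the best score.** Change = value − baseline, and the value cannot be below 0, so the lowest change is −baseline. Zero is best only when baseline is 0.

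- AN count: inclusion criterion 9 ("Have a total AN count of" at least 5) puts the lowest change at −5 or below. Not affected.
- IHS4 = nodules + 2 × abscesses + 4 × draining tunnels (SAP 5.4.2.3). With AN of at least 5, the minimum baseline is 5 × 1 = 5. Not affected.
- Abscesses: no entry minimum. Affected at baseline 0.
- Draining fistulas: only an upper limit (exclusion criterion 24, "Has a draining fistula count of >20 at the baseline visit"). Affected at baseline 0.
- Inflammatory nodules: five abscesses and no nodules is eligible. Affected at baseline 0.
- HSSD-24h pain: items start at 0 and entry sets no minimum. Affected at baseline 0.

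So four of the six endpoints can be affected. The MMRM includes baseline and baseline-by-visit terms, which lessen the effect without removing it.

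**Size in one arm (unadjusted means).** Arm sizes follow from planned numbers: 75/3 = 25 at the first interim analysis and 150/3 = 50 at full Part 1 enrolment. The actual Week 16 numbers are not in the documents. One failure at +d scored as 0 lowers the arm mean by d/n.

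- d = 2 lesions: 2/25 = 0.08; 2/50 = 0.04.
- IHS4 going from 5 nodules to 5 nodules, 1 abscess and 1 draining fistula: 5 + 2 + 4 = 11, so d = 6; 6/25 = 0.24; 6/50 = 0.12.

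**Size between arms.** Shift in bermekimab minus placebo = −(k_B − k_P) × d/n, where k is the number of failures. Lower is better, so a positive shift counts against bermekimab.

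- Assumed 1 on bermekimab, 3 on placebo, d = 2: −(1 − 3) × 2/25 = +0.16; with n = 50, +0.08.
- Counts reversed: −0.16 or −0.08.
- Equal counts: 0.

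With assumed failure fractions f and mean post-event change m, the shift is −(f_B − f_P) × m.

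- 5% v 20%, m = +4: −(0.05 − 0.20) × 4 = +0.60.
- 20% v 5%, m = +4: −0.60.
- 20% v 5%, m = −3 (participants who had improved): +0.45.

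The sign depends on which arm has more failures and whether they had worsened or improved. The documents settle neither.

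**What is already reported.** SAP 5.2 tabulates reasons for stopping intervention by group through Week 16. SAP 5.6.2 tabulates and lists AEs leading to discontinuation. SAP 6.5 lists participants meeting ICE 2. Together these largely give the number of assigned values by arm. What stays hidden is the size of the values replaced.

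**The case for a change.** The best case for a change is that it costs little. Part 1 lesion counts are weekly and HSSD-24h daily to Week 16, so no new data are needed. One could keep the zero rule and add a second MMRM that assigns the larger of zero and the last change observed up to the event. It never scores better than the main rule and it preserves recorded worsening. Abscess and fistula change could also be shown among participants with baseline above 0.

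The two situations are real, and it is true that no output shows how much was replaced. The proposed remedy is weaker than it looks:

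- It carries forward one observation and keeps only upward noise. If true change is 0 and the observed change has an SD of 1 to 3 lesions (assumed), the expected added value is SD/√(2π), or 0.40 to 1.20 per affected participant. With three failures on one arm and one on the other at n = 25, noise alone creates 2 × 0.40/25 = 0.03 to 2 × 1.20/25 = 0.10. Against the 0.16 illustrated above, that is 20% to 60%. A difference from the main result could not be put down to the zero rule.
- A baseline-above-0 report limited to abscesses and fistulas leaves out nodules and pain.

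Extending the treatment-policy analysis would be the better choice, but it is also imperfect. Protocol 7.1 says participants who stop "will continue to return for protocol-specified procedures and evaluations for approximately 5 weeks following the last administration of study intervention", so a last dose before about Week 16 − 5 = 11 leaves no Week 16 value. The MMRM would still use the visits that were made, but its missing-at-random assumption is debatable after treatment failure. After ICE 2, observed values may also reflect the other therapy.

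Denying credit to participants who had improved before the event is not a fault: a no-benefit composite is meant to do that.

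**Conclusion.** This is a fair trade-off, and the plan can stand. The zero rule is explicit, consistent and defensible as a no-benefit score, and each alternative brings a disputable assumption of its own.

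The illustrated shifts are 0.08 to 0.16 lesions between arms for three failures against one at +2 lesions, up to 0.60 in either direction under the more extreme assumed rates, and nil when rates and post-event changes are equal. All rest on assumed failure counts and sizes, and on planned arm sizes of 25 to 50.

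No conclusion depends on the answer. SAP 5.4.1 makes these p-values nominal, and HiSCR50 does not use the rule. Participants with ICEs 1-2 are non-responders in the HiSCR and HS-IGA analyses, and worsening appears in the AE tables. The protocol calls for robustness analyses of the primary endpoint (9.4.2.1.3) but leaves additional secondary analyses optional (9.4.2.2). The futility decision had been taken before this SAP, which was cut back for that reason (SAP 6.2). A statistician who wants more can run the same MMRM on observed post-event data as an optional, low-priority extra, with ICE 1-2 counts by arm beside it.
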